Hypertensive patients who have severe sleep apnea (apnea hypopnea index or respiratory disturbance index > 25 events/hour) will be studied to allow the greatest likelihood of detecting significant differences in outcome variables. We will take patients who are and who are not using CPAP and will stratify their randomization based on baseline CPAP use. This will be done to simulate real-world treatments as best as possible and determine if our therapies' effectiveness is modified by CPAP use. All subjects will undergo a screening visit (Visit 1) at their local site to determine eligibility and collect pertinent data. Subsequently, subjects will be randomized to one of the three treatment groups (allopurinol, losartan, or placebo) and will have a physiology and vascular baseline study completed (Visit 3).

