4.1 Inclusion Criteria

Inclusion Criteria

- Males and females between ages of 21 and 65 years inclusive
- Apnea hypopnea index or respiratory disturbance index (RDI) greater than or equal to 25 events/hour (diagnosed by Polysomnography or home study)
- Subjects eligible for CPAP or BiPAP therapy. If subject is on CPAP or BiPAP, he/she must be on treatment for a minimum of 3 months prior to Visit 2.
- Hypertension by clinical history of high blood pressure readings or diagnosis of hypertension (may be controlled with non-exclusionary medications) or average blood pressure \geq 140/90 mm Hg (only require systolic OR diastolic to be above threshold, not both for inclusion). Blood pressures used for inclusion based on average blood pressure \geq 140/90 mm Hg will be (using two measurements in prior 12 months – in PHI or other records OR 1 prior elevated blood pressure and 1 blood pressure at screening)

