4.2 Exclusion Criteria

Exclusion Criteria

- If subject not using CPAP, having AHI $>$ 60 events/hour or oxygen saturation \leq 65% during sleep
- Presence of clinical CV disease (coronary artery disease, angina, arrhythmias (subjects with sinus arrhythmias will be reviewed by PI for enrollment), stroke, TIA, cor pulmonale, etc.), heart failure, bruits, or diabetes mellitus by clinical diagnosis/history
- Presence of pulmonary disease that results in significant hypoxemia (resting SaO₂ $<$ 88%)
- Hypertriglyceridemia (triglycerides $>$ 300 mg/dL).
- Diabetes (fasting plasma glucose $>$ 125 mg/dL)
- Subjects taking angiotensin converting enzyme inhibitors, angiotensin receptor antagonists, renin inhibitors, potassium-sparing diuretics (without accompanying loop/thiazide diuretic), allopurinol, oxypurinol, febuxostat, amoxicillin, ampicillin, azathioprine or mercaptopurine. *(see below for examples)
- Subjects with chronic kidney disease (Serum creatinine $>$ 1.5 mg/dL) or history of significant hyperkalemia (Serum potassium $>$ 5.2 mEq/L) with ARB therapy
- Subjects with history of angioedema
- Subjects with bilateral, modified radical or radical mastectomies
- Subjects who have a Serum potassium $>$ 5.0 mEq/L at the screening visit
- Female subjects who are pregnant (determined by urine pregnancy test) or breastfeeding
- Subjects with active MRSA or VRE (vancomycin resistant enterococcus) infection
- History of adverse reaction to allopurinol, losartan, or zolpidem**
- Subjects who are currently receiving cancer treatment or have received cancer treatment in the past 1 year.
- Subjects who cannot swallow oral capsules
- Subjects who are hospitalized or who have been recently hospitalized (last 2 weeks)

Version: 23, 7-25-17

- Inability to comply with or complete the protocol or other reasons at the discretion of the investigators

*angiotensin converting enzyme inhibitors (lisinopril, enalapril, etc.)

Angiotensin receptor antagonists (losartan, valsartan, etc.)

Renin inhibitors (aliskiren)

Potassium sparing diuretics (spironolactone, eplerenone, triamterene without hydrochlorothiazide, etc.)

**If adverse reaction to zolpidem, may opt out of control of breathing study

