4.3 Subject Recruitment and Screening

Screening Visit (Visit 1): Subjects will come to the CRU or their local recruitment site for a brief screening visit. **Subjects should be instructed to be fasting for at least 12 hours prior to their visit and patients should hold any blood pressure medications on the morning of VISIT 1 (they may take at end of VISIT or after).** Investigators will explain the study, answer questions, and complete the informed consent and HIPAA process. Potential subjects identified through sleep databases and registries will be contacted via telephone to obtain verbal consent or declination for participation in this study. A waiver of written documentation of informed consent has been approved by the IRB to obtain consent via telephone. At the in person screening visit, the subject will then sign a consent form witnessed by the study coordinator or investigator. The subject will then receive a signed copy of this consent form. All copies of the consent forms will be maintained in the subject's binder. The subject will then undergo:

- a history and physical with the CRU nurse practitioner
- undergo a 12-lead electrocardiogram (if the electrocardiogram has abnormalities of clear clinical significance, then a copy of the EKG with a letter explaining those abnormalities will be sent to the subject with instructions to share with his/her physician).
- take a urine pregnancy test (for females of child-bearing age),
- have a fasting blood sample taken to measure serum cholesterol, potassium, creatinine, uric acid, and glucose concentrations

If the subject declines participating in the study, any personal and health related information will not be retained and will be destroyed upon completion of the telephone call.

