Subjects will not receive study medications until the end of Visit 3 and will be instructed to bring their study medication bottles with them to Visit 4 (two weeks after starting medication) and Visit 6 (6 weeks after starting medication). Study drug diary evaluation will be used to evaluate study drug adherence. Subjects will receive an auto-CPAP machine or CPAP compliance card to use during the study. Subjects will not receive payment for Visit 6 if they do not return the CPAP machine or CPAP compliance card. Subjects will be instructed to maintain the baseline CPAP use throughout the study. Subjects will complete baseline 24-hour ambulatory blood pressure monitoring (Visit 2) prior to receiving either study drug. This will take place prior to their overnight visit to Madison (Visit 3).

Study subjects will be recruited from the Wisconsin Sleep Center in Madison, Marshfield Clinic in the greater Marshfield, WI area, Aurora Bay Care in Green Bay, and Gundersen Health System in La Crosse, WI. Wisconsin Sleep initiated a research subject registry and database in August, 2008, and the subject registry invites all patients referred to clinic or laboratory to consider being contacted about research projects. Data that is maintained in the subject database includes patient name, date of birth, gender, contact information, sleep study data, and diagnoses. Drs. [name] and [name] will also recruit subjects at Wisconsin Sleep in their own clinics. Subjects will be recruited in clinics at Wisconsin Sleep and after their sleep study at Wisconsin Sleep or

Version: 23, 7-25-17

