after a home study done by Wisconsin Sleep. Additional advertisements will be made available to subjects at other Sleep laboratories and clinics in the area, as well as at other clinics and medical centers in the greater Madison area (including, but not limited to: Baraboo sleep lab/clinic, Sauk prairie hospital sleep lab/clinic, St. Mary's sleep lab/clinic, Portage sleep lab/clinic, Reedsburg sleep lab/clinic, etc. Permission will be obtained prior to posting flyers or advertisements. An opt-out letter will be sent to qualifying subjects and the subjects will have 7 days to opt out before we will contact them to provide further information about the study and inquire as to their interest. Additional subjects who have participated in previous studies by investigators or other research groups who have expressed interest in future sleep apnea studies will be contacted about this study. Recruitment will also be completed with the use of social media and the internet. We will advertise on the UW Job Board, Craigslist, and Wisconsin Sleep's website. We will implement an email blast to the UW Madison students, faculty and staff as well as use campus and local newspapers and other media.

Recruitment at other sites:

We will also recruit from the sleep laboratories and sleep clinics at Marshfield Clinic, Marshfield, WI, Gundersen Health System, La Crosse, WI, and Aurora Bay Care, Green Bay, WI. Subjects will be recruited by the responsible investigators at the individual sites with the help of study coordinators. Subjects will be identified following sleep studies in the sleep laboratories and during visits to clinic. Subjects will be contacted and approached about study participation by individuals involved in his/her clinical care. Subjects may also be identified using advertisements in the community and at the local medical centers if necessary.

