5.5.1 CPAP Before and During Study

Subjects who are using CPAP or BiPAP prior to the study will be asked to provide adherence data for the time period prior to them entering the study. Subjects who require CPAP or BiPAP must be on treatment for a minimum of 3 months prior to Visit 2. This information will be obtained from their CPAP/BiPAP machine or from their home health provider that services their CPAP/BiPAP machine. We will also ask for their permission to contact their sleep physician to obtain a copy of their sleep study report. This will help us to determine how severe their sleep apnea is. Consent to obtain this information from home health providers and sleep physician will be obtained in the informed consent document. Subjects who qualify for the study will be instructed to continue to use CPAP/BiPAP the same amount during the study as they were using prior to the study. If subjects are not using CPAP/BiPAP prior to study entry, they will be instructed to continue not using CPAP/BiPAP during the study.

At Visit 3, subjects will be given a CPAP machine or CPAP compliance card to use during the study. Subjects using BiPAP will continue to use their own BiPAP machine. We will set the pressure on this machine to the same pressure the subject was using on their machine at home. Subjects will bring their CPAP/BiPAP machine or compliance card with them to Visit 4 (at local site) and Visit 6 (in Madison) to have the adherence data checked. Investigators should remove the compliance card from the CPAP machine and download the data at Visits 4 and 6. After the download, the cards should be returned to the subjects' CPAP machines. Subjects will use the mask they had previously been using with the CPAP/BiPAP machine issued to them. The Respiration CPAP machines given to subjects during the study will be capable of measuring residual breathing events to determine how effectively the machine is treating a subject's sleep apnea.

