6.2 Summary of Visits

Subjects may complete some, but not all procedures without a protocol deviation occurring or affecting their study eligibility. For logistical or other reasons, subjects may complete some of the procedures (but not all procedures) (i.e. in cases of non-exclusionary subject disabilities that preclude them from having certain procedures done or body habitus that does not allow completion of certain procedures.). Reimbursement for participation will be pro-rated for Visits 3 and 6 as in protocol section 11.2.

Visit 1: Screen Visit (will be performed at each respective recruitment site)

- informed consent, height and weight, heart rate, blood pressure, temperature, and electrocardiogram recorded, blood samples, urine pregnancy test, brief history (performed by study coordinator and local PI)
- physical examination (local PI and UWHC medical staff (i.e., physician, physician's assistant, or nurse practitioner) for Madison subjects)

Visit 1A: If visit 2 will occur more than 90 days after visit 1, subjects will undergo repeat screening procedures in a separate visit to the local study site (Visit 1A) including:

Medical history, medication history, birth control assessment, blood samples, urine pregnancy test, AE assessment, electrocardiogram recorded (performed by the local PI, study coordinator, or medical staff (i.e., physician, physician's assistant, or nurse practitioner)

Visits 2 and 5: Home Blood Pressure Monitoring (will be performed at each local site where subjects were originally enrolled)

- Receive blood pressure monitor and Holter/heart rate variability monitor* to wear for 24 hours along with the diary recording of activity each time they engage in activity and each time the blood pressure cuff inflates; subject returns to the study site the following day (all activities performed by coordinator-local PI consulted if necessary). Subjects at UW-Madison will come to the School of Pharmacy Clinical research space of the Office of Clinical Trials Examination Space (H6/136 CSC) to be set up with their 24-hour blood pressure cuff and Holter/heart rate variability monitor. Adverse events will be assessed at visits 2 and 5.

Version: 23, 7-25-17

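### The Visit 3 sleep study can show a subject off CPAP to be beyond the protocol's own severity limit, yet no rule in the available text requires anyone to check or to lift the no-CPAP instruction

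*Combined protocol and SAP*

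**What the plan says.** - **Limit.** The exclusion in section 4.2 begins "If subject not using CPAP, having AHI" and continues with more than 60 events/hour, or saturation of 65% or lower in sleep. It names no source sleep study and no maximum age for one.
- **When eligibility is judged.** Section 3.1: "All subjects will undergo a screening visit (Visit 1) at their local site to determine eligibility and collect pertinent data". Section 5.4 places randomization at the end of that visit.
- **What Visit 1 contains.** Section 4.3 lists history and physical, ECG, pregnancy test and bloods ("have a fasting blood sample taken to measure serum cholesterol, potassium, creatinine, uric acid, and glucose concentrations"). No sleep study is listed there or under Visit 1 in section 6.2.
- **Where entry severity comes from.** Section 4.1 takes AHI or RDI as "diagnosed by Polysomnography or home study". Section 5.5.1 seeks permission to obtain the earlier report so as to judge severity, with no threshold attached.
- **Recruitment routes.** Section 4.3 says of one source that "Wisconsin Sleep initiated a research subject registry and database in August, 2008"; that database holds sleep study data. Of the other sites it says: "Subjects will be identified following sleep studies in the sleep laboratories and during visits to clinic".
- **Re-screening after 90 days (Visit 1A, section 6.2).** "Medical history, medication history, birth control assessment, blood samples, urine pregnancy test, AE assessment, electrocardiogram recorded". No sleep study is repeated.
- **Visit 3.** Section 3.1 schedules full polysomnography on night one, expressly to establish OSA severity. Section 6.2 puts dispensing on day two, followed by the night-two breathing study with zolpidem.
- **Instruction to non-users.** Section 5.5.1: "If subjects are not using CPAP/BiPAP prior to study entry, they will be instructed to continue not using CPAP/BiPAP during the study".

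**The concern.** The protocol judges that subjects above a certain severity should not be studied while off CPAP. Just before treatment starts, it measures that severity in its own laboratory, and in the available text nothing follows from the result. Anyone following that text under the Visit 1 reading could dispense drug, supply zolpidem for night two and leave the instruction to stay off CPAP in place, although the study's own measurement lies beyond its own limit.

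What is at stake is participant protection. Non-users were untreated before they enrolled, so the protocol does not create their non-use. The issue is that a study instruction stays in force after the study holds information that its own exclusion treats as disqualifying.

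**Working it through.** There is no planned figure to reproduce. The check sets the sections side by side, with some arithmetic on the schedule and on spare sample size.

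**1. Is the limit re-applied at Visit 3?**

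| Criterion | At entry | Explicit action at Visit 3 |
|---|---|---|
| Bruit | Section 4.2 exclusion | Yes: section 6.2 ends participation |
| Pregnancy | Section 4.2 exclusion | Yes: section 5.6.1 tests before dispensing |
| AHI/saturation, non-CPAP | Section 4.2 exclusion | None found, although night one measures both |

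The bruit row is the most informative. Bruit is already an exclusion in section 4.2, yet section 6.2 states the consequence again for Visit 3. For that criterion the authors did not rely on section 4.2 alone to carry forward.

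**2. Does another section require action?**
- Section 4.4.1 has triggers for creatinine, potassium, blood pressure and adverse effects. It has none for AHI or saturation. Termination at the physicians' judgment is possible but not prompted by the sleep study.
- Section 4.2 ends with an investigator-discretion exclusion, which is also permissive.
- Section 6.5 opens with non-exhaustive wording, but its sentence on sending a letter covers only ECG, cardiac output and serum tests.
- Section 8.1 counts an abnormal diagnostic result as an adverse event if, among other grounds, the investigator thinks it clinically significant. That does not require the result to be looked at.

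**3. How long does the instruction run?** Section 5.2 gives days 1 to 42, so 42 days of treatment. Visit 4 is at about day 14, leaving 42 − 14 = 28 days. Neither Visit 4 nor Visit 5 lists a measure of sleep severity. Polysomnography is next done at Visit 6, after treatment.

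**4. How old could the entry study be?** From the registry's start in August 2008 to the version date of 25 July 2017 is 107 months; 107 / 12 ≈ 8.9 years. This shows only that the text sets no age limit. It is not a typical age.

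**5. What room is there for losses?** Section 7.1 plans 100 randomized and bases power on 20 complete MSNA datasets per group. 100 / 3 = 33.3 per arm; 33.3 − 20 = 13.3 per arm; 13.3 / 33.3 = 40%. How much of this is already taken by drop-out and failed recordings is not stated.

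**6. How many subjects are affected?** Not computable. The documents give no share of non-users, no distribution of entry severity or age of sleep studies, and no night-to-night variation in AHI.

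**The case against.** The case on the other side is substantial.

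- **The rule may be in an appendix.** Section 6 refers to Appendix 2, and section 14 lists Appendix 1 as the procedure descriptions. Neither was in the available text. This stands, and it limits the claim to the sections that could be read.
- **Eligibility is settled at Visit 1.** A reader might infer that the severity limit belongs to no visit at all. Section 3.1 does not support that: it makes Visit 1 the eligibility visit, and several other section 4.2 bullets name no visit either. The ordinary reading is that severity is judged at entry from the diagnostic study.
- **Section 4.2 may be a standing exclusion.** If so, a subject known to exceed the limit would be excluded once the result was seen. That is a fair reading and gives staff grounds to act. On either reading, though, no one is told to look at the result before dispensing.
- **The comparators differ.** A bruit is found at once and may signal unrecognised cardiovascular disease; pregnancy testing is tied to the drugs' pregnancy ratings. The documents describe no hazard of losartan or allopurinol that depends on AHI. This argues against automatic withdrawal of drug. It does not justify keeping the no-CPAP instruction in place.
- **A repeat cut-off after randomization has a price.** AHI varies from night to night, and nothing shows that it is scored by the next morning. A reader might infer that every subject over the limit must be withdrawn. The documents do not support that, and it would cost randomized subjects on the strength of one night.

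**Conclusion.** The point holds as a gap in participant protection. In the available text, the Visit 3 polysomnogram measures the quantities in the section 4.2 limit before drug is dispensed, no rule requires the comparison, and section 5.5.1 can keep a subject beyond the limit off CPAP for the six-week study.

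Per affected subject, the exposure is 42 days under the instruction. The number of such subjects is unknown and may be small. The conclusion rests on two assumptions: that section 4.2 is applied at Visit 1, and that Appendices 1 and 2 contain no check.

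Three stronger inferences are not supported:
- that entry sleep studies are in fact years old: other subjects are approached after a sleep study, and no ages are given;
- that the protocol makes subjects untreated: they were not using CPAP on entry;
- that the primary analysis, sample size or endpoint is in error: nothing here bears on them.

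**What to change.** In section 6.2, require that for subjects not on CPAP the Visit 3 AHI and saturation be reviewed against the section 4.2 limit before dispensing, or as soon as scored. If the limit is exceeded:

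- lift the section 5.5.1 instruction to stay off CPAP, notify the subject and refer for treatment;
- omit the night-two zolpidem study if the result is known by then;
- have the blinded study physician decide whether study drug is withheld or stopped, with no automatic withdrawal.

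Add polysomnography to the findings reported under section 6.5. Keep these subjects in the ITT set, report them by arm with the reason, and record any start of CPAP. If Appendix 1 or 2 already contains the check, a cross-reference is enough.

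**Cost.** Protocol wording, and review of data already recorded. A few subjects may be lost, or may change CPAP use, after randomization, some only because of night-to-night variation in AHI. If scoring is slow, some will have started drug. Starting CPAP matters for interpretation, since section 1.1 credits it with effects on sympathetic activity; section 7.2 already plans a regression on hours of CPAP use. The trigger is measured before any drug is taken and reviewed blind, so it should not depend on arm. The nominal margin of about 13 per arm gives some room, though part of it may already be used.

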5.6 Prior and Concomitant Therapy

Information about all medications (prescription, OTC and supplements) being taken will be collected at Study visits 1, 1A, 2, (if more than 90 days after Visit 1), 3, 4, 5, 6, and 7. Subjects are instructed to let the study coordinator know if they start any new medication while they are enrolled in the trial. Other antihypertensive agents (diuretics, calcium channel blockers – see Appendix 3 for allowable blood pressure medications) will be allowed but doses should remain constant during the study period. Subjects taking non-hypnotic benzodiazepines, narcotic analgesics, quetiapine, or barbituates, on a daily basis or have taken them within 5 days (when using them p.r.n. (pro re nata or as needed) before the control of breathing study will not be allowed to participate in the control of breathing study (night 2, visits 3 and 6). However, if a subject is taking a medication for sleep (e.g. hypnotic benzodiazepines, zaleplon, eszopiclone, etc.), they may participate in the control of breathing study if zolpidem may be taken instead of their usual sedative hypnotic for the control of breathing study. Subjects should not take PDE-5 inhibitors (ie. sildenafil (Viagra), vardenafil (Levitra), or tadalafil (Cialis) within 72 hours (3 days) before or after taking nitroglycerin. If a subject has taken any of these medications within that timeframe he/she will not be able to participate in the [name] lab portion of Visit 3.

The following medications are not allowed to be taken:

Angiotensin converting enzyme inhibitors, angiotensin receptor antagonists, renin-inhibitors, potassium-sparing diuretics, allopurinol, oxypurinol, febuxostat, amoxicillin, ampicillin, azathioprine or mercaptopurine.

